Children's exposure to violent and nonviolent discipline was assessed using the MICS Child Development and Child Disciplinary modules. Exposure to violent disciplinary practices was defined as having experienced as a cumulative score of the number of forms of violent discipline

Intimate Partner Violence

Intimate partner violence among parents who are currently married, cohabitating, and/or in a relationship was assessed using an adapted and abbreviated version of the revised Conflict Tactics Scale (CTS-2: Strauss, 2004) previously used in Rwanda (Chaudhury et al. 2016). The CTS-2 assesses caregivers' self-reported victimization and perpetration of emotional neglect/abuse, physical assault, and sexual assault. Given the short interval between the baseline and midline data collection, the scale was adapted so that caregivers report on events that occurred within the last three months and ever (as opposed to 12 months in the original scale). For events that had happened, caregivers further report on the frequency of that event using the following scale: 0="not at all"; 1="once"; 2="Twice"; 3="3-5 times"; 4="6-10 times"; 5="11-20 times"; 6=">20 times." Overall, the same events are asked for victimization and perpetration with the exception that two additional sexual assault questions were asked about for victimization (detailed below). The following examples refer to victimization. After the questions about victimizations, caregivers were asked similar question for perpetration stated as "You [left you or forgot] your partner" etc.

Two items assess emotional abuse or neglect: "Your partner used abusing language toward you" and "She/he left you or forgot you." Seven items assess physical abuse : "She/he shoved you,"

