VUP-status [classic public works vs. expanded public works]	Government records
OUTCOME VARIABLES	
Malawi Developmental Assessment Tool (MDAT)	
Gross motor [standardized score]	MDAT
Fine motor [standardized score]	MDAT
Language [standardized score]	MDAT
Social [standardized score]	MDAT
Ages and Stages Questionnaire (ASQ-3)	
Gross motor [delayed/not delayed]	ASQ-3
Fine motor [delayed/not delayed]	ASQ-3
Communication [delayed/not delayed]	ASQ-3

Personal social [delayed/not delayed]	ASQ-3
Problem solving [delayed/not delayed]	ASQ-3
Anthropometrics	
Height-for-age (HAZ)	Anthropometrics
Weight-for-age (WAZ)	Anthropometrics
Weight-for-height (WHZ)	Anthropometrics
Middle upper arm circumference (MUAC)	Anthropometrics
"Father engagement "	
" father spends time every day caring for the child"	HOME
Family Violence	
Violent discipline [cumulative score, 0-7]	MICS-5 Hash discipline module
Intimate partner violence	
Victimization physical and sexual abuse past 3 months [cumulative score 0-7]*	Conflict Tactics Scale- CTS2
Perpetration physical and sexual abuse past 3 months [cumulative score 0-7]**	Conflict Tactics Scale- CTS2

*Among cohabitating or married mothers only

**Among cohabitating or married fathers only

***Among cohabitating or married caregivers only

Table 2. Study predictor and outcome variables.

Data Analysis Plan

Standard descriptive statistics will be used to describe the study sample. Frequencies and percentages will be reported for categorical variables and mean, median, standard deviation, interquartile range, maximum and minimum values will be reported for continuous variables. Anthropometric data will be cleaned for extreme out-of-range values. Scales will be created from individual items according to scoring instructions for each scale. All scales will be evaluated for psychometric properties. Visual inspection of histograms and other plots will be used to identify outliers.

Continuous Outcomes MDAT, WAZ, MUAC, WHZ: The goal is to determine the efficacy of SM at 12 months from study initiation. Measurements of all outcome variables (see Table 2 and Section B), are taken at baseline, midline (4 months post baseline), and endline (12 months post midline). Subjects are randomized (Section B) into a treatment group (SM) and CG. Effectiveness will be determined if the slope of the response variable for the SM group is significantly different than the slope of the CG group. To test this hypothesis, we will fit a linear

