In fitting logistic mixed effect regression models, it is possible that we may run into numerical difficulties in computing a likelihood ratio test, so score type tests may be needed. This is more likely to occur in the case of testing for variance components.

Count Outcomes, harsh discipline, physical and sexual violence: These metrics count types of harsh discipline action or physical and sexual abuse as suffered or inflicted. Our experience with these scales is that there are more values of zero than what would be predicted by a standard

Poisson distribution. Our analysis will make use of Zero Inflated Poisson (ZIP) models (Everitt, & Hothorn, 2005; Long, 1997). These models belong to the more general class of mixture models. In particular they model the binomial probability of a count of zero versus a count greater than zero and the Poisson probability for counts greater than zero. In particular we will fit mixed effect models as described in the continuous variable sections but under the ZIP distribution assumption.

A key difference between a mixture model and more standard probability distributions is the fixed effects structure and tests for significance can vary between the two parts (binomial and Poisson). Likelihood ratio testing for the Time*Treatment group interaction will be performed for both components of the mixture model. A significant result of the LRT test for the binomial portion would indicate that the probability of no violence (inflicted or suffered) differed between the treatment groups. A significant result of the LRT on the Poisson portion of the ZIP model would indicate that among those who inflicted or suffered harsh discipline or violence the mean amount of violence differed between the treatment groups. The two portions are contained in a single likelihood function and parameter estimation is done simultaneously.

Model Assumptions and Alternative Tactics: The key assumption in these models is the ZIP distribution of the response variables. We will visually inspect the distribution of the outcome variables to verify that we are fitting the correct model. Alternative distributions could be Poisson, Quasi-Poisson, Binomial (data dichotomized due to lack of variability), or Negative Binomial. These are non-mixture models and modeling will follow the process outlined in the continuous outcomes section.

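### The violence scores are capped counts of types, but the plan fits an uncapped zero-inflated Poisson model and reads its count part as the amount of violence among those affected: that reading is wrong, and the standard errors are not assured

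*Combined protocol and SAP*

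**What the plan says.** **Discipline.** Section B (Violent discipline) defines the outcome as "a cumulative score of the number of forms of violent discipline", and Table 2 lists it as "Violent discipline [cumulative score, 0-7".

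**Partner violence.** Section B (Intimate Partner Violence) states "Seven items assess physical abuse", then lists three sexual items for victimization and one for perpetration. Each event that occurred also gets a frequency code, on a scale from 0 to 6. The section calls the outcome a count of events, leaves out the emotional items, and declines midpoint frequency scoring because it is too skewed. Table 2 gives "Victimization physical and sexual abuse past 3 months [cumulative score 0-7" and "Perpetration physical and sexual abuse past 3 months [cumulative score 0-7".

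**Model.** The Count Outcomes part of the Data Analysis Plan says "These metrics count types of harsh discipline action or physical and sexual abuse as suffered or inflicted" and then "Our analysis will make use of Zero Inflated Poisson (ZIP) models", with the same mixed-effect structure as the continuous outcomes. The Time × Treatment interaction gets a likelihood ratio test in each part. A significant binomial part is to mean that the probability of no violence differed. A significant Poisson part is to mean that "among those who inflicted or suffered harsh discipline or violence the mean amount of violence differed between the treatment groups".

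**Safeguards.** The plan names the ZIP distribution as its key assumption and will check it by looking at the outcome distribution. The fallbacks, described as non-mixture models, are Poisson, quasi-Poisson, binomial on dichotomized data, and negative binomial.

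**The concern.** A score that counts how many listed forms occurred cannot exceed the length of the list. Its variance depends on the number of items, how common they are and how strongly they go together. A Poisson part has no maximum and sets the variance equal to the mean. Zero inflation deals with surplus zeros, not with the ceiling or the spread of the rest. If the variance is wrong, so is the error rate of the tests behind Hypothesis 1(c).

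The second issue needs no assumptions. The plan fixes in advance how a significant result will be worded, and that wording claims something that neither the score nor the model measures.

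**Working it through.** **The plan's own figure.** None is given for the violence outcomes. The only power statement concerns the linear model, and it is consistent. With 200 clusters of 5 and an ICC of 0.10, the effective number per arm is 500/(1 + 4 × 0.10) = 357. A two-sided test at 0.05 then has 91.6% power at 0.25 (at least 90% stated) and 83.6% at 0.22 (at least 80% stated). The point here does not depend on it.

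**1. Is the score capped?** Discipline: yes, 0-7, one point per form. Partner violence: summed frequency codes could reach 6 × 10 = 60 (victimization) and 6 × 8 = 48 (perpetration), which does not fit 0-7. The wording about types and the rejection of midpoint scoring point the same way. However, yes/no scoring of the listed items gives maxima of 7 + 3 = 10 and 7 + 1 = 8, not 7. Seven matches the physical items alone.

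**2. What can the count part show?** Let λ be the mean of the Poisson part and π the always-zero share.
- Zeros inside the Poisson class: exp(−λ), which is 37% at λ = 1 and 14% at λ = 2.
- Mean among those with any: λ/(1 − exp(−λ)), which is 1.58 at λ = 1 and 2.31 at λ = 2. Halving λ from 2 to 1 therefore changes that mean by a ratio of 1.58/2.31 = 0.68, not 0.50.
- Probability of no violence: π + (1 − π)exp(−λ). With π = 0.40 (assumed) and λ = 1 this is 0.40 + 0.60 × 0.368 = 0.62, so the binomial part alone does not determine it either.

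The plan's two readings describe a hurdle model. In addition, a partner-violence report that falls from more than 20 episodes to one on the same items leaves the score unchanged.

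**3. Variance against Poisson.** For m yes/no items with prevalence p and inter-item correlation ρ, variance/mean = (1 − p)(1 + (m − 1)ρ); Poisson requires 1. For m = 7 and ρ = 0:

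| Mean score | Variance/mean | Poisson SE too large by | ρ at which the ratio is 1 |
|---|---|---|---|
| 1 | 0.86 | 8% | 0.03 |
| 2 | 0.71 | 18% | 0.07 |
| 3 | 0.57 | 32% | 0.125 |

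Above the ρ in the last column, the Poisson SE is too small. The ceiling itself matters little at low means: the Poisson probability above 7 is 0.1% at mean 2 and 1.2% at mean 3.

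**4. Simulation.** Null effect, 500 per arm, one wave, no random effects, 40% structural zeros, 300 replicates. Entries are ZIP count-part model SE divided by the true SE, with type I error at a nominal 5% (Monte Carlo error about 1.3 points). The item prevalences, the correlations and the structural-zero share are assumptions.

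| Items, p | ρ = 0 | ρ = 0.05 | ρ = 0.1 | ρ = 0.2 |
|---|---|---|---|---|
| 7, 0.15 | 1.07 (4.0%) | 0.99 (5.0%) | 0.93 (6.3%) | 0.82 (11.3%) |
| 7, 0.30 | 1.19 (2.0%) | 1.06 (4.3%) | 1.02 (4.7%) | 0.92 (8.7%) |
| 7, 0.45 | 1.28 (1.0%) | 1.30 (0.7%) | 1.15 (2.3%) | 1.00 (4.7%) |
| 10, 0.15 | 1.09 (3.7%) | 0.96 (6.3%) | 0.89 (8.3%) | 0.74 (15.0%) |
| 10, 0.30 | 1.10 (3.7%) | 0.94 (6.3%) | 0.93 (8.0%) | 0.81 (12.0%) |
| 10, 0.45 | 1.36 (0.0%) | 1.15 (2.0%) | 0.94 (7.3%) | 0.84 (12.0%) |

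More extreme settings widen the range. Seven unrelated items at p = 0.5 with 30% structural zeros give ratios of 1.34-1.40 and type I error of 0.7-0.8%. Eight to ten items with ρ = 0.2-0.3 and 50-60% structural zeros give 0.70-0.83 and 10-19%.

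**5. Cost of the conservative case.** If the SE is k times too large, a test with 80% power at the correct SE has power P(Z < 2.80 − 1.96k). That is 65% at k = 1.23 and 52% at k = 1.40.

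**The case against.** A reader might infer that the error bars are simply wrong, or that the trial will report false effects on violence. The documents do not support that, for four reasons.

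- **Unknown inputs.** They give neither mean scores nor item correlations, only the prevalence of any violent discipline in a background survey (19.8% at 0-11 months, 80.7% at 24-36 months). Several plausible cells in the table are close to 1.
- **A simpler model was simulated.** The plan has three waves and random effects. A three-wave null simulation of 1,000 families, fitted with a family random intercept but no cluster effects or random slopes (160 runs per setting, Monte Carlo error about 2 points), gave ratios of 0.93-0.96 and type I error of 6-7% for partner violence when item correlation was mostly persistent within families. With correlation wholly wave-specific it was 0.83 and 10%; wholly persistent, 1.26 and 2%. Unrelated discipline items stayed conservative (1.29 at p = 0.5, 1.06 at p = 0.2), because random effects add variance and cannot remove it.
- **Fallbacks exist.** Quasi-Poisson rescales the SE in either direction, and negative binomial handles overdispersion.
- **The score is legitimate.** Counting types is a reasonable way to test Hypothesis 1(c), so the interaction test is not invalid in itself.

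All of this stands and limits the claim about standard errors. Three gaps remain. The visual check has no decision rule. Quasi-Poisson gives up the zero part and, as the plan concedes for quasi-binomial models, the likelihood ratio test. Binomial is offered only for dichotomized data, so no listed option keeps the full score within its maximum. None of the four reasons rescues the stated interpretation.

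**Conclusion.** The point holds in two parts of different strength. The interpretation rule is wrong as written, whatever the data look like: the count part cannot show an amount of violence, nor does it describe only those with any. The standard errors are not assured rather than shown to be wrong. Under assumed inputs, and without the planned waves and random effects, they range from about 35-40% too large to about 20-30% too small, with near-correct values in between. The planned family effects would absorb much of the second error, but not the first.

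For partner violence the conclusion rests on reading the outcome as a count of items endorsed, which the 0-7 range and the wording about types support but the Measures text leaves open. The example of falling frequency applies to partner violence only, since no frequency scale is described for discipline. This should be corrected before analysis; it does not show that the planned test is invalid.

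**What to change.** 1. **Define the scores.** State that each item scores yes/no, and reconcile Table 2's 0-7 range with the 10 victimization and 8 perpetration items in Section B. Do this first: any bounded model needs the maximum.
2. **Change the basis for inference.** Test Time × Treatment with a method that does not rely on Poisson variance. One option is the mean number of types with cluster-robust standard errors, which is practical with the 48 + 38 + 112 = 198 retained clusters. It gives one overall test, zeros included, instead of two parts. The other is a bounded mixed model (zero-inflated binomial or beta-binomial). The bounded model was not tested here, so it is an option rather than a requirement. Replace visual inspection with a numeric dispersion check, giving its threshold and the action that follows.
3. **Reword the interpretation.** Report the count part as the number of different forms in the class that is not always zero. If statements about those with any violence are wanted, use a hurdle model.

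Cost: revised SAP text, a little more model code, one extra dispersion parameter if the beta-binomial is chosen, and possible convergence work with a short score and several random effects. No new data are needed.

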Hypothesis Aim 1 (a): Children in families participating in Sugira Muryango will demonstrate improved developmental outcomes. Specifically, children from families who received Sugira Muryango will score better on assessments of cognitive, language, and socioemotional development compared to children in the control group (CG).

Hypothesis Aim 1 (b): Children in families participating in Sugira Muryango will display improved physical growth compared to children in the control group (CG). Specifically, we expect to see improvement in weight-for-age, weight-for-height, upper middle arm circumference. We do not expect to see large improvements in height-for-age over this relative short time frame.

Hypothesis Aim 1 (c): Caregivers who participate in Sugira Muryango will report lower levels of family violence (intimate partner violence and harsh discipline) compared to children in the control group (CG).

Hypothesis Aim 1 (d): Among families with a father present in the child’s life, families receiving Sugira Muryango will show greater levels of father engagement in caring for the child compared to children in the control group (CG).

Gaps in Knowledge

Throughout sub-Saharan Africa, integrating scalable, cost-effective ECD and violence prevention programs into poverty-reduction and other social welfare programs has great potential

for promoting ECD and reducing familial violence in culturally diverse, low-resource settings. Data from the Sugira Muryango (SM) trial will support and advance the Rwandan government's vision for comprehensive decentralized ECD to help eradicate poverty and violence against children. The objectives of this research seek to contribute to academia and research institutions' roles and responsibilities outlined in the ECD Policy housed under the Ministry of Gender and Family Promotion (MIGEPROF, 2016).

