assumption does not hold across time (baseline, 3 months, and 12 months) we can treat time as a categorical variable to examine differences between the treatment groups at individual time points focusing on the 12-month group differences adjusted for baseline. If examination of panel plots reveals a large amount of heterogeneity among trajectories of the outcomes by subjects we can use Growth Mixture Models which first identify clusters of similar trajectories from which we can test for treatment group differences in terms of membership in the clusters of similar trajectories.

Outliers will be flagged through visual inspection and standardized residual values greater than 3. A sensitivity analysis will be done to determine if outlier removal changes the coefficient values. If we find that outliers are having an oversized effect on the estimated coefficient values we will give preference to the models where the outliers are removed. However, we will present both results.

Some responses are scales or derivations of scales in particular the MDAT and the ASQ. We will examine the psychometric performance of these scales. We are especially concerned with internal consistency and item reliability. If these scales do not show at a minimal amount of internal consistency (Cronbach's Alpha > 0.6) these items will not be considered for analysis. If particular items are an issue they may be dropped from the scale. Research, in areas like Rwanda suffer because standard scales have not been validated on these populations.

Binary Outcome ASQ, shared decision making, father engagement: The analysis for these outcomes will be similar to the analyses above with accommodations being made for the fact the ASQ is a binary outcome. In particular, we will have to make use of mixed effect logistic regression models a form of generalized linear mixed models (GLMM) with a binomial distribution and a logistic link. Outside of accounting for the correct distribution of the response variable the analysis will follow the methods outlined in the previous MDAT section.

Model Assumptions and Alternative Tactics: We will examine Pearson residuals to assess goodness of fit. Alternative methods include the use of quasi-binomial mixed effects regression (in the case of over dispersion). However, such models do not have a full likelihood and instead of LRT test we will have to rely on the Wald-type type test for regression coefficients.

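### Violence counts: the plan names a zero-inflated Poisson model but reads its binomial part as a test of the probability of no violence, which holds only for a hurdle model

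*Combined protocol and SAP*

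**What the plan says.** Section D, Count Outcomes, covers violent discipline and physical and sexual partner violence, which Table 2 lists as scores from 0 to 7. The text chooses a ZIP model, places it among mixture models and has both parts estimated in one likelihood.

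- On the two parts: "they model the binomial probability of a count of zero versus a count greater than zero and the Poisson probability for counts greater than zero".
- On the longitudinal structure: "we will fit mixed effect models as described in the continuous variable sections but under the ZIP distribution assumption".
- On testing: "Likelihood ratio testing for the Time*Treatment group interaction will be performed for both components of the mixture model".
- On interpretation: if significant, the "LRT test for the binomial portion would indicate that the probability of no violence (inflicted or suffered) differed between the treatment groups".
- On fallbacks: "Alternative distributions could be Poisson, Quasi-Poisson, Binomial (data dichotomized due to lack of variability), or Negative Binomial". The dichotomised binomial is tied to a lack of variability.

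No hurdle model and no contrast in the overall probability of a zero is planned. The analyses serve Hypothesis Aim 1(c), that participating caregivers "will report lower levels of family violence (intimate partner violence and harsh discipline" than controls.

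**The concern.** Two different models are mixed in one paragraph. A hurdle model splits the data into zero versus positive, then models the positive counts with a zero-truncated distribution. Its binomial part is a test of any violence versus none. A ZIP model mixes a class that is always zero (probability π) with an ordinary Poisson class (mean λ) that can also yield zeros. Its binomial part concerns π alone. The plan names the second and describes the first.

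If a hurdle model was meant, software called for ZIP will fit something else. If ZIP was meant, the stated interpretation does not follow from the test.

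The stake is a wrong label on an outcome under Aim 1(c). Suppose Sugira Muryango (SM) reduces the number of forms of violence in violent homes and leaves the share of violence-free homes unchanged or slightly higher. Applying the stated rule can then yield a report that the probability of no violence differed, with the estimate pointing to fewer violence-free homes under SM.

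**Working it through.** The plan gives no figure for the count outcomes, so there is none to reproduce.

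**Algebra.** In a ZIP model P(0) = π + (1 − π)exp(−λ). The binomial test asks whether π changed differently by arm; P(0) depends on λ as well. All π and λ values below are assumed.

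| Case | π, λ at start | π, λ at end under SM | P(0) at start | P(0) at end under SM |
|---|---|---|---|---|
| A | 0.30, 1.5 | 0.185, 1.1 | 0.3 + 0.7e^−1.5 = 0.456 | 0.185 + 0.815e^−1.1 = 0.456 |
| B | 0.30, 1.5 | 0.20, 1.0 | 0.456 | 0.2 + 0.8e^−1.0 = 0.494 |
| C | 0.30, 1.5 | 0.40, 1.5 | 0.456 | 0.4 + 0.6e^−1.5 = 0.534 |
| D | 0.30, 1.5 | 0.30, 1.1 | 0.456 | 0.3 + 0.7e^−1.1 = 0.533 |

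In A, π falls and P(0) does not move. In B, π falls and P(0) rises. In C the plan's reading is true. In D, P(0) rises and π does not move.

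**Sample sizes.**
- The Randomization Plan targets at least 1,040 households: 1,040/2 = 520 per arm.
- Power and Sample Size gives 5 families per cluster and an ICC of 0.10 (set for the linear model, borrowed here). Design effect = 1 + (5 − 1)(0.10) = 1.4, so 520/1.4 = 371.
- For partner violence, an assumed 300 cohabiting or married respondents per arm gives 300/1.4 = 214.

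**Time.** The Data Analysis Plan places the later waves at "midline (4 months post baseline), and endline (12 months post midline", that is 0, 4 and 16 months. The alternative-tactics text for continuous outcomes says the "assumption does not hold across time (baseline, 3 months, and 12 months". Since 4/16 = 3/12 = 0.25, a linear-time interaction test is the same under either schedule.

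**Simulation.** Maximum-likelihood ZIP with intercept, arm, time and arm × time in both parts; three waves; equal baselines; independent observations; 1-df likelihood ratio test at 3.841. There were 1,500 trials per cell in A and 1,000 in the others (standard error at most 1.6 points). Log λ is linear in time under SM. In A, π is solved at each wave so that P(0) stays at 0.456 (midline λ 1.388, π 0.275).

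Rejection rates at n = 520, 371 and 214 per arm:

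| Case | ZIP binomial part | Any versus none |
|---|---|---|
| A: P(0) equal throughout | 37%, 30%, 18% | 4–5% |
| B: P(0) higher under SM | 29%, 23%, 14% | not tabulated |
| C: reading true | 34%, 27%, 17% | 46%, 37%, 23% |
| D: effect through λ only | 5% throughout | 44%, 34%, 20% |

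In A, at least 98% of rejections pointed to fewer structural zeros under SM. In B, at least 96% of rejections had the wrong sign for P(0).

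**Variations on A.**
- Two waves only: 38%, 29%, 19%.
- Full effect reached by midline: 34%, 27%, 16%.
- Random-intercept ZIP fitted to correlated family data: 39%, 25%, 17%. Intercept SDs were 1.0 on logit π and 0.5 on log λ, P(0) was 49.6% in both arms, and 800 trials were run per n.
- Four other equal-P(0) settings: 17–30%, 13–23%, 10–16%.
- A smaller effect (λ 1.5 to 1.3, π 0.30 to 0.252; P(0) = 0.252 + 0.748e^−1.3 = 0.456): about 10–13%, 7–10% and 6% over two runs.

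**The case against.** The strongest reply has four parts.

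1. The plan says only that the probability of no violence differed, without a direction. If the effects oppose but do not cancel, P(0) does differ and the sentence is literally true. This stands: the sentence is strictly false only under cancellation, as in A. Case B shows a risk in directional reporting.
2. If SM works through both parts as hypothesised (π up, λ down), both changes raise P(0), and the reading and its sign are right. With π 0.30 to 0.40 and λ 1.5 to 1.1, the binomial part rejected in 27%, 23% and 12% of trials. The sign was correct in every rejection at the two larger sizes and in about 94% at n = 214. This also stands. Case A needs SM to lower the odds of being a structural zero: (0.185/0.815)/(0.30/0.70) = 0.53. Nothing in the documents shows that this is likely.
3. The larger rates come from cuts in λ of 25–27%, and with a small cut the rate approaches 5%. In A the Poisson part also rejected in 80%, 61% and 38% of trials, so the reduction in amount would usually be reported as well. Both points limit how often harm would arise. Neither makes the binomial statement correct.
4. The dichotomised binomial fallback is a direct any-versus-none model. It replaces ZIP only when variability is lacking, so it does not check this reading.

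Case D contradicts no sentence in the plan. It shows a loss of sensitivity only.

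**Conclusion.** The concern holds. The named model and the description of its parts do not agree, and under the named model a significant binomial test does not establish that the probability of no violence differed. This follows from the formula for P(0) and needs no assumed values.

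How often it would mislead does depend on assumptions. Where P(0) was equal in both arms, the binomial part rejected in between about 6% and 39% of simulated trials, depending on effect size and n, against a nominal 5%. In case A and its same-effect variations, nearly all rejections pointed to fewer structural zeros under SM.

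The documents supply no π or λ. Cluster effects, random slopes and the public-works term were not simulated, and clustering enters only through the effective n. The plan's reading is correct when π rises and λ does not, and also when π rises and λ falls. No claim is made about its reading of the Poisson part. The plan should be corrected before these outcomes are interpreted.

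**What to change.** Make the model name and the description agree, in one of two ways.

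- **Hurdle.** Specify a mixed hurdle model: logistic for any versus none, plus a zero-truncated Poisson or negative binomial for positive counts. The planned interpretation of the binomial part can then stay.
- **ZIP.** Keep ZIP, describe the binomial part as the probability of a structural zero, and draw any no-violence conclusion from the model-based contrast between arms in P(0). That contrast uses both parts, averages over the random effects, and carries a delta-method or bootstrap interval.

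The cost is SAP wording plus a different model call (hurdle) or one post-estimation contrast (ZIP). No additional data are needed. The drawback of the ZIP route is the extra computation for averaging and the interval.
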